#### **Publications**

A publication can be a journal manuscript, an abstract, a poster/presentation for a congress, or any openly accessible material.

A primary publication including the primary results of the trial (i.e. the results of the primary endpoint[s]) will be submitted for peer-reviewed publication within 12 months of database lock. LEO Pharma is responsible for this publication. All authors (trial responsible employees and/or applicable investigators and advisors) must fulfill the criteria for authorship from the International Committee of Medical Journal Editors (ICMJE).

The investigators may reach out to LEO Pharma to publish results that are not included in the primary publication. The investigator and LEO Pharma should agree on terms for data sharing and collaboration on such publications, as well as timing for release of the publication(s). In all cases, LEO Pharma retains the right to review and comment on the draft publication in due time before submission, but the investigator is not required to revise the draft accordingly, unless it discloses company confidential information or protected personal information, or may compromise intellectual property rights of LEO Pharma.

LEO Pharma may give researchers outside LEO Pharma access to anonymised data from this trial for further research according to the principles outlined by the European Federation of Pharmaceutical Industries and Associations (EFPIA) (46). In that case, the researchers are obliged to attempt publication of the results obtained from their analyses.

LEO Pharma complies with Good Publication Practice (GPP3) standards and the recommendations from ICMJE.

Page 104 of 121

#### **Appendix 3F: Insurance**

LEO Pharma has taken out relevant insurances covering the subjects in the present clinical trial in accordance with applicable laws and regulations.

## Appendix 3G: Financial disclosure

Investigators will provide LEO Pharma with sufficient, accurate financial information as requested to allow LEO Pharma to submit complete and accurate financial certification or disclosure statements to the appropriate regulatory authorities. Investigators are responsible for providing information on financial interests during the course of the clinical trial and for 1 year after completion of the clinical trial, or for a longer period of time if required by local legislation.

#### Appendix 3H: Trial and trial site closure

#### Premature termination of trial or trial site

LEO Pharma, the investigator, the IRBs/IECs, or competent authorities may decide to stop the clinical trial, part of the trial, or a trial site at any time, but agreement on procedures to be followed must be obtained.

If a clinical trial is suspended or prematurely terminated, the investigator must inform the subjects promptly and ensure appropriate therapy and follow-up. As specified by applicable regulatory requirements, the investigator or LEO Pharma must promptly inform IRBs/IECs and provide a detailed written explanation. Relevant competent authorities must be informed.

The trial must be terminated if the perception of the benefit/risk ratio (judged from clinical signs and symptoms, [S]AEs, and/or remarkable safety laboratory changes) becomes unfavourable for the continuation of the trial.

Reasons for the premature closure of a trial site by LEO Pharma or investigator may include but are not limited to:

- Failure of the investigator to comply with the protocol, the requirements of the IRB/IEC or local health authorities, LEO Pharma procedures, or GCP guidelines.
- Inadequate recruitment of subjects by the investigator.

Page 105 of 121

#### **Completion of trial**

Trial sites will be closed upon trial completion. LEO Pharma will undertake arrangements for the collection and disposal of any unused trial material that the investigator is not required to keep in his/her files. A trial site is considered closed when all required documents and trial supplies have been collected and a trial site closure visit has been performed.

#### **Appendix 3I: Responsibilities**

The signatory investigator is responsible for the approval of the clinical trial protocol and the CTR on behalf of all clinical trial investigators and as agreed to in a signatory investigator agreement.

The national coordinating investigators are responsible for national issues relating to the clinical trial as agreed to in a national coordinating investigator agreement.

**Each participating investigator** is responsible for all aspects of the clinical trial conduct at his/her trial site as agreed to in a clinical trial agreement.

Page 106 of 121

# **Appendix 4: Country-specific requirements**

#### France

This appendix describes requirements and procedures that are specific for France. The text from the protocol is presented in normal font. The specific country requirements or procedures are presented below in bold font.

#### Section 8.3 Exclusion criteria

Subjects are not eligible for the trial if they fulfil any of the following criteria:

5. Subjects not affiliated with or not a beneficiary of a social security scheme.

#### Canada

As per Health Canada standards, all essential trial documents and source documents will be archived for 15 years.

Page 107 of 121

# Appendix 5: Short version of eligibility criteria

	Inclusion criteria		
No.	Short version		
1	Signed and dated informed consent has been obtained prior to any protocol-related procedures.		
2	The baseline visit in this extension trial must coincide with the Week 16 (end-of-treatment) visit in the parent trial.		
3	Subjects must have met eligibility criteria at screening and baseline in the parent trial (LP0133-1401 or LP0133-1402).		
4	Subjects must have completed the treatment period in the parent trial (to be assessed at baseline visit in this extension trial).		
5	Subjects must have complied with the clinical trial protocol in the parent trial to the satisfaction of the investigator.		
6	A woman of childbearing potential must use an acceptable method of birth control throughout the trial up until the end-of-treatment/early termination visit.		

Exclusion criteria		
No.	Short version	
1	Subjects who prematurely discontinued treatment with IMP or initiated rescue treatment in the parent trial (LP0133-1401 or LP0133-1402).	
2	Subjects who experienced any AE during participation in the parent trial, which precludes further treatment with delgocitinib cream 20 mg/g in the judgement of the investigator.	
3	Any medical or psychiatric condition that could put the subject at undue risk by participating in the trial, or which, by the investigator's judgment, makes the subject inappropriate for the trial.	
4	Current participation in any other interventional clinical trial, except for parent trial.	

Page 108 of 121

## Appendix 7: COVID-19 pandemic contingency plan

Without compromising the safety of subjects and trial integrity, it is expected that efforts are made to secure attendance at sites for all visits, ensuring important safety and efficacy assessments for the trial.

If on-site visits are not possible due to local authority-issued preventive measures, the affected site will postpone screening and enrolment of subjects (Week 12 and Week 16 in the parent trials) until on-site visits can be conducted. For already enrolled subjects, post-baseline visits can be done remotely via phone or video. At phone/video visits, no investigator assessments of efficacy can be done. Decisions to start or stop treatment with delgocitinib cream 20 mg/g will be at the investigator's discretion based on the outcome of the phone/video visit and the decision will be documented on a separate eCRF page. This option can only be used in case of local authority-issued preventive measures related to COVID-19 that would prevent the subjects from attending an on-site visit. The following data will be collected remotely (according to the schedule of trial procedures in Section 4):

- AE reporting.
- Treatment application (daily completion in the eDiary).
- Concomitant medication and concurrent procedures.
- Subject assessment of local tolerability (daily completion in the eDiary while on treatment).
- HESD (daily completion in the eDiary).
- PROs (HEIS, DLQI, EQ-5D-5L, WPAI-CHE). The subjects will receive a link to the PROs in a web browser and will complete them from their own computer.
- New CHE lesions.
- Urine pregnancy test. Women of childbearing potential will receive 1 extra urine
  pregnancy test at the baseline visit to keep at home in case on-site visits become
  impossible during the trial. The subject will take the test at home and inform the
  investigator about the result via phone. Additional urine pregnancy tests can be
  shipped to the subject's home together with IMP (see below) if needed.

Page 110 of 121

In the eCRF, it will be recorded whether a visit or a given assessment was done remotely or not done. If not done, it will be recorded if this was due to the pandemic.

It will be at the discretion of the investigator to decide whether clinical laboratory samples are considered necessary to ensure subject safety in periods when on-site visits are not possible. If possible, a home visit can be arranged for a healthcare professional to collect relevant clinical laboratory samples.

Contingency plans due to COVID-19 must follow the authorities' COVID-19 guidelines and local requirements. Written procedures describing the contingency plan must be in place at site/depot. To ensure availability of IMP, the trial sites will dispense additional IMP if considered relevant (i.e. if local authority-issued preventive measures are to be expected at the given trial site). This will allow subjects to continue treatment with IMP although they are not able to go to the trial site. If a subject will not be able to attend on-site visits due to the pandemic before running out of IMP, the trial site will ensure shipping of IMP to the subject's home.

If a subject is tested positive for COVID-19, the investigator will evaluate whether this is an AE that contraindicates further dosing, in which case the subject will permanently discontinue IMP as described in Section 10.

Page 111 of 121

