During the trial, the investigators will be trusted to take appropriate actions to ensure the safety of the individual subjects according to local authority-issued preventive measures. As these can differ across countries and regions, no general instruction from the sponsor can be provided concerning subject safety and the need for postponing trial visits. In case of local authority-issued preventive measures, the investigator can convert on-site visits into phone or video consultations. At phone/video visits, no investigator assessments of efficacy can be done. Therefore, if and only if subjects are prevented from attending on-site visits due to local authority-issued preventive measures, a decision to start or stop treatment with delgocitinib 20 mg/g can be taken based on a phone or video visit. Safety monitoring remains an obligation to LEO Pharma, and it is considered feasible to collect safety data remotely (via electronic communication) where on-site visits are not possible. Other mitigating measures include collecting patient-reported outcome (PRO) data via a web-based solution and ensuring supply of IMP to the subjects to overcome local authority-issued preventive measures due to the COVID-19 pandemic (see Appendix 7 for details).

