## Reporting in eCRF

For each time treatment with delgocitinib cream 20 mg/g is started or stopped as per the investigator's assessment, the date of first and last application of delgocitinib cream 20 mg/g will be recorded.

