## 14.3.6 Analysis of other/exploratory endpoints

All analyses are based on safety analysis set.

The number of on-treatment days from baseline up to Week 36 will be summarised.

The number of on-treatment periods from baseline up to Week 36 and the rates per 100 person years of observation time will be presented.

The proportion of response days (days with IGA-CHE 0 or 1) from baseline up to Week 36 will be summarised. Mean duration of on-treatment periods per subject from baseline up to Week 36 will be summarised.

Time to first IGA-CHE score ≥2, initiation of rescue treatment, or discontinuation of IMP, whichever occurs first, will be presented for the subjects in the safety analysis set who were previously treated with delgocitinib cream 20 mg/g twice daily in the parent trial and achieved IGA-CHE TS at Week 16 in the parent trial. Kaplan-Meier curve and estimates will be presented. Subjects will be censored at the date of the last assessment visit in case of no events. Follow-up time to first IGA-CHE score ≥2 starts from the baseline visit.

Time to first response (IGA-CHE 0 or 1) will be presented for the subjects in the safety analysis set who did not achieve IGA-CHE TS at Week 16 in the parent trial, by treatment group assigned in the parent trial (delgocitinib cream 20 mg/g or cream vehicle respectively). Kaplan-Meier curves and estimates will be presented. Subjects will be censored at the date of the last assessment visit, initiation of rescue treatment, or discontinuation of IMP, whichever occurs first. Follow-up time to first response will be derived from the baseline visit.

Time to response (IGA-CHE 0 or 1) following treatment re-initiation after first off-treatment period will be presented for subjects in the safety analysis set who were treated with delgocitinib cream 20 mg/g twice daily in the parent trial. Kaplan-Meier curves and estimates will be presented. Subjects will be censored at the date of the last assessment visit, initiation of rescue treatment, or discontinuation of IMP, whichever occurs first. Follow-up time to response will be derived from the visit of treatment re-initiation after first off-treatment period.

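### Cream started at a COVID-19 phone or video visit has no IGA-CHE score, so if such starts occur the exploratory time-to-relapse curve would date those relapses late, miss them or censor them

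*Combined protocol and SAP*

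**What the plan says.** Section 5.5 provides that, if and only if local authority measures keep a subject from attending on site, "a decision to start or stop treatment with delgocitinib 20 mg/g can be taken based on a phone or video visit". Appendix 7 repeats the restriction, adds that "Decisions to start or stop treatment with delgocitinib cream 20 mg/g will be at the investigator's discretion", and sends the decision to its own eCRF page. Of these visits it says: "At phone/video visits, no investigator assessments of efficacy can be done".

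Section 14.3.6 defines the relapse analysis as "Time to first IGA-CHE score ≥2, initiation of rescue treatment, or discontinuation of IMP, whichever occurs first". It applies to subjects who received delgocitinib in the parent trial and had IGA-CHE treatment success at its Week 16. With a score of 0 or 1 at baseline, they enter this trial off cream (Sections 7.1 and 9.3.1). The censoring rule is "Subjects will be censored at the date of the last assessment visit in case of no events".

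For time to response after re-initiation, Section 14.3.6 says: "Follow-up time to response will be derived from the visit of treatment re-initiation after first off-treatment period". Section 7.1 defines re-initiation as triggered by IGA-CHE ≥2 after a score of 0 or 1 in this trial.

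Under Section 9.8.4 (Reporting in eCRF), for each start or stop by the investigator's assessment, "the date of first and last application of delgocitinib cream 20 mg/g will be recorded".

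**The concern.** An on-site start of cream requires IGA-CHE ≥2, so on site the start and the relapse event fall together. A remote start separates them: the investigator has judged that the disease needs treatment, but none of the three events in Section 14.3.6 has happened. No analysis section uses the remote-decision eCRF page, and Section 14.3.13 imputes nothing outside binary responses.

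The curve is the trial's description of how long remission lasts after cream is stopped. If treated relapses are delayed or lost, it describes a mixture of untreated remission and time on cream.

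The re-initiation analysis has a related gap. A remote restart has no score and so does not meet the Section 7.1 definition, which leaves the start of follow-up unclear for that course.

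**Working it through.** **Reading the rules together.** The plan states no expected relapse rate, remote-visit rate or power for this endpoint, so there is no figure to reproduce. Take a responder who is off cream, relapses, and starts cream at a remote visit. Under Section 14.3.6 as written:

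- Next on-site IGA-CHE ≥2: the event is counted, but dated at that later visit.
- Next on-site IGA-CHE 0 or 1 on cream: this relapse is not counted, and the subject stays at risk as relapse-free. A later relapse can still be counted.
- No later on-site score: the subject is censored although already relapsed. The plan does not define *last assessment visit*. If it means the last scored visit, the time on cream drops out of the risk set, but the censoring is informative.

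Each branch raises the curve. The exception is a remote start for disease that would have scored below 2.

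**Illustrative size.** From the plan: scheduled visits every 4 weeks to Week 36. Assumed: exponential time to relapse with median 8 weeks; a fraction *p* of visits remote (5%, 10% or 20%); probability *c* (0.4 to 0.6) of a score of 0 or 1 at the next on-site visit on cream, after which the relapse clock restarts; subjects without an event followed to Week 36.

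True relapse-free share: S(t) = 2^(−t/8). This gives 35.4% at Week 12, 12.5% at Week 24 and 4.4% at Week 36.

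Per 4-week interval the relapse probability is h = 1 − 2^(−4/8) = 0.2929. Let A be the share off cream and relapse-free, and B the share on cream after a remote start with no event recorded. At each visit:

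- A(next) = A(1 − h) + B(1 − p)c
- B(next) = A·h·p + B·p
- Recorded relapse-free share = A + B

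With p = 0.10 and c = 0.4:

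- Week 4: A = 0.7071; B = 0.2929 × 0.10 = 0.0293.
- Week 8: A = 0.7071 × 0.7071 + 0.0293 × 0.36 = 0.5105; B = 0.7071 × 0.0293 + 0.0293 × 0.10 = 0.0236.
- Week 12: A = 0.5105 × 0.7071 + 0.0236 × 0.36 = 0.3695; B = 0.5105 × 0.0293 + 0.0236 × 0.10 = 0.0173.
- Recorded share = 0.387 against a true 0.354, a gap of about 3 points.

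The same calculation for the other inputs, checked by simulation, gives these gaps in percentage points over c = 0.4 to 0.6:

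| Remote visits | Week 12 | Week 24 | Week 36 |
|---|---|---|---|
| 5% | about 2 | 1 to 1.5 | under 1 |
| 10% | 3 to 4 | 2 to 3 | 1 to 2 |
| 20% | 7 to 9 | 5 to 7 | 3 to 4 |

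**Alternative model.** Suppose instead that each relapse is seen in the week it occurs, as the unscheduled-visit rule intends; that 5%, 10% or 20% of relapses are handled remotely; and that c is 0.4 to 0.7. The Week 16 share (median 8 weeks) then reads about 27%, 28% to 29% and 30% to 33%, against a true 25%. Counting the remote start as an event removes the gap in both models.

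**Against sampling error.** The documents do not give the parent allocation. Assume 600 enrolled, allocation 1:1 or 2:1, and treatment success of 30% to 50% (around the phase 2b 39.0%). The curve then has between 600 × 1/2 × 0.30 = 90 and 600 × 2/3 × 0.50 = 200 subjects. The standard error at 35.4% is √(0.354 × 0.646/n), which is 5.0 points at n = 90 and 3.4 at n = 200.

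**The case against.** The strongest reply is that this may never matter. The remote option exists only under authority-issued measures, Appendix 7 asks for efforts to secure attendance at all visits, and nothing shows that a remote start occurred. At 5% remote visits the Week 12 shift is under one standard error, and at 10% it is about one. The endpoint is exploratory, with no test or decision attached. Section 14.3.12 also lets the sponsor settle the handling in an amendment, the SAP or the CTR. All of this stands. It limits size and priority, but does not supply the missing rule.

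It is also fair that an unscored, discretionary start is a weaker event than IGA-CHE ≥2 and could err the other way. That is why a second curve is needed. But rescue treatment and IMP discontinuation already count without a score, so admitting an unscored event is not foreign to this endpoint.

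A reader might infer more than the documents support:

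- *Every remotely treated subject is carried as relapse-free while on cream.* Some are counted late, and some may leave the risk set by censoring.
- *The plan favours the drug throughout.* There is no comparator. In the response analyses, failing to count a remote stop would delay response, which works against the drug.
- *Remote restarts are dropped from the re-initiation analysis.* The text is ambiguous: follow-up starts at the visit of re-initiation, a remote visit may be one, and application dates are recorded.

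**Conclusion.** The gap holds in conditional form. If remote starts occur, Section 14.3.6 as written dates those relapses late, misses them or censors them, and the relapse-free curve is biased upward for those subjects, except where disease would have scored below 2. The flat statement that time to relapse is overstated would be tempting, but it needs a count of remote starts that the documents do not give.

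The gaps in the table rest entirely on the assumed median, remote share and clearance probability. They show the order of size and are not estimates for this trial. For re-initiation, the finding is that the start of follow-up is unclear for a remote restart. Minor priority.

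**What to change.** In Section 14.3.6 or the SAP:

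1. Count a cream start recorded on the remote-decision eCRF page as a relapse event on that visit's date, alongside the three existing events. Give a sensitivity curve using the existing events only.
2. Define the last assessment visit as the last visit with an IGA-CHE score.
3. For time to response after re-initiation, start follow-up at the recorded remote restart date where the restart was remote.
4. Show the response curves with and without remote stops counted as response.
5. Report the number of remote starts and stops.

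The cost is SAP wording and some programming on data already collected. No visit, assessment or treatment rule changes. Because an on-site start already requires IGA-CHE ≥2, item 1 alters remote cases only. The downside is that a remote start is an event without a confirming score, so a few may be for disease that would have scored below 2. The sensitivity curve and the counts let a reader judge that.

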## **Appendix 8: Acceptable methods of birth control**

Acceptable methods of birth control include:

- Bilateral tubal occlusion or ligation (tubal sterilisation methods).
- Intrauterine device.
- Intrauterine hormone-releasing system.
- Combined (oestrogen- and progestogen-containing) hormonal contraception associated with inhibition of ovulation (oral, intravaginal, transdermal).
- Progestogen-only hormonal contraception (associated with inhibition of ovulation [oral, injectable, implantable] or without inhibition of ovulation as the primary mode of action [oral]).
- Sexual abstinence (when this is in line with the preferred and usual lifestyle of the subject and not just being without a current partner).
- Same-sex partner.
- Vasectomised partner (given that the subject is monogamous).
- Male or female condom with or without spermicide.
- Cap, diaphragm, or sponge with spermicide.

Page 112 of 121

# Appendix 9: Assessments performed at baseline and screening in the parent trials

## **Demographics**

The following demographic data will be recorded:

- Date of birth. If full date of birth is not allowed to be recorded, month and/or year (as allowed by local legislation) of birth should be collected together with the subject's age.
- Sex: female, male.
- Ethnic origin (self-reported by the subject): 'Hispanic or Latino', 'not Hispanic or Latino'.
- Race (self-reported by the subject): American Indian or Alaska Native, Asian –
  Chinese, Asian, Black or African American, Native Hawaiian or other Pacific
  Islander, White, other (requires a specification to be provided). More than 1 race
  can be recorded per subject in the eCRF.

